9.4.1 Entry Criteria (Table 4)	Hepcidin was removed as an entry criteria assessment	
8.2.1.2 Iron Stopping Criteria	Amended to allow the Investigator to use his clinical judgement and removed TSAT and ferritin values as discontinuation criteria.	The intent of the iron stopping criteria is to ensure participants remain on the same dose of oral iron supplement throughout the study. Therefore, the stopping criteria was amended to allow the Investigator to use his clinical judgement to determine if a

Section # and Name	Description of Change	Brief Rationale
		participant's iron supplement required adjustment.
5.4 Scientific Rationale for Study Design	Removed mention of absolute change in Hemoglobin to define the evaluable population	Hemoglobin variability is managed through the hgb stopping criteria
10.3.1.3 Evaluable Population	Deleted the criterion of absolute changes from baseline (Day 1 pre dose) in haemoglobin ≤ 0.75 g/dL from the evaluable population definition	
12.3 Appendix 3 Risk Assessment	Drug Interaction information updated	Modified to maintain consistency with current Risk Assessment
12.7 Appendix 7 Contraceptive Guidance and Collection of Pregnancy Information	Urine pregnancy testing kit sensitivity corrected from 2 mIU/mL to 25 mIU/mL	To correct typographical error.

TABLE OF CONTENTS

	PAGE
PROTOCOL AMENDMENT SUMMARY OF CHANGES TABLE.....	3
1. SYNOPSIS.....	8
2. SCHEDULE OF ACTIVITIES (SOA).....	10
3. INTRODUCTION.....	12
3.1. Study Rationale	12
3.2. Background	13
3.3. Benefit/Risk Assessment	13
3.3.1. Risk Assessment	13
3.3.2. Benefit Assessment	14
3.3.3. Overall Benefit:Risk Conclusion	14
4. OBJECTIVES AND ENDPOINTS.....	14
5. STUDY DESIGN	15
5.1. Overall Design	15
5.2. Number of Participants	16
5.3. Participant and Study Completion.....	16
5.4. Scientific Rationale for Study Design	16
5.5. Dose Justification.....	18
6. STUDY POPULATION	18
6.1. Inclusion Criteria	18
6.2. Exclusion Criteria.....	19
6.2.1. Hgb Stability Criteria	21
6.3. Lifestyle Restrictions.....	22
6.4. Screen Failures.....	22
7. TREATMENTS.....	23
7.1. Treatments Administered.....	23
7.1.1. Daprodustat Dosing Information	24
7.1.2. rhEPO Dosing Information	24
7.1.3. ⁵⁷ Fe Dosing Information	24
7.1.4. ⁵⁸ Fe Dosing Information	24
7.2. Dose Modification	25
7.3. Method of Treatment Assignment.....	25
7.4. Blinding.....	25
7.5. Preparation/Handling/Storage/Accountability	25
7.6. Treatment Compliance.....	26
7.7. Concomitant Therapy.....	26

1. SYNOPSIS

Protocol Title: A repeat dose, open label, two period, randomized, cross over study to compare the effect of daprodustat to recombinant, human erythropoietin (rhEPO) on oral iron absorption in adult participants with anemia associated with chronic kidney disease who are not on dialysis

Short Title: Anemia Studies in CKD: Erythropoiesis via a Novel PHI Daprodustat – Iron (ASCEND-Fe)

Rationale: Several proteins involved in iron absorption/metabolism are known to be HIF target genes. In this regard, daprodustat is equipotent against 3 human PHD enzymes (PHD1, PHD2 & PHD3) thereby stabilizing both HIF1 α and HIF2 α . Increased iron absorption correlates with increased expression in enterocytes and proerythroblasts of divalent metal-iron transporter 1 (DMT1), duodenal cytochrome b561 (DcytB) and ferroportin (FPN) mRNA. HIF-2 α is reported to up-regulate the expression of these genes by direct binding to consensus hypoxia response elements (HRE). Thus, there is the potential that daprodustat administration, by virtue of increasing HIF levels, can increase oral iron absorption and incorporation into Hgb. Therefore, the purpose of this study is to compare the effect of daprodustat to rhEPO (i.e., epoetin alfa or darbepoetin alfa) on non-heme oral iron absorption using stable isotopic iron (^{57}Fe & ^{58}Fe) by measuring incorporation of iron in erythrocytes.

Objectives and Endpoints:

[figure not shown]
Objectives	Endpoints
Primary	

 Compare the efficacy of daprodustat to rhEPO (i.e., epoetin alfa or darbepoetin alfa) on iron absorption 	
 Difference in fractional oral iron absorption (%) between daprodustat and rhEPO
Secondary	

 Characterize the effect of daprodustat or rhEPO on markers of iron status 	
 Change from baseline (Day 1) at 14 and 28 days following treatment with daprodustat or rhEPO in serum iron, transferrin, transferrin saturation, soluble transferrin receptor, ferritin, hepcidin and erythroferrone

 Characterize the effect of daprodustat or rhEPO on indices of erythropoiesis 	
 Change from baseline (Day 1) at 14 and 28 days following treatment with daprodustat or rhEPO in Hgb, hematocrit, red blood cell number, mean corpuscular volume, reticulocyte Hgb and reticulocyte number

Objectives	Endpoints
Safety	

 Assess safety and tolerability 	
 Incidence and severity of adverse events and serious adverse events Reasons for discontinuation of study medication Vital signs assessments

Overall Design: This study will be a randomized, repeat dose, open label, two period cross-over study in adult, male and female participants with anemia associated with chronic kidney disease who are not on dialysis currently treated with stable doses ($\leq 50\%$ change in 4-weekly dose) for at least 8 weeks prior to and including the screening period, of rhEPO (i.e., epoetin alfa or darbepoetin alfa).

Number of Participants: Sufficient participants will be enrolled such that at least 12 participants comprise the Evaluable Population.

Treatment Groups and Duration:

- There will be a 4-week screening period in order to confirm that participants have stable Hgb levels and to assess entry criteria
- A 28-day Treatment Period 1 for incorporation of iron into erythrocytes while on randomized study treatment
- A 28-day Treatment Period 2 for a second incorporation of iron into erythrocytes while on randomized study treatment
- A follow-up visit 14 ± 3 days after completing treatment.

2. SCHEDULE OF ACTIVITIES (SOA)

Procedure	Screening ¹		Treatment Period ²					Follow-up ¹
	Week -4	Week -2	Day 1	Day 15	Day 29 ³	Day 43	Day 57	Day 70
Informed Consent	X							
Entry Criteria	X ⁴	X ⁴	X ⁴					
Physical, Medical History, Demography, Height	X ^{5,9}	X ^{5,9}	X ^{5,9}					
Weight	X		X	X		X		
HemoCue Hgb	X	X	X	X	X	X	X	
eGFR	X							
Females: Urine Pregnancy Test ⁶	X		X		X		X	X
Females: Estradiol & FSH ⁷		X						
HIV screening and Hepcidin	X							
Randomization			X					
Administration of isotopic iron				X		X		
Blood sampling for isotopic iron					X	X	X	
Crossover ⁸					X			
ECG		X						X
Vital signs	X		X		X		X	X
Clinical chemistry & hematology ¹⁰	X							X
Urinalysis ¹⁰	X							X
Liver chemistry monitoring ¹¹				X		X		
Folate & Vitamin B ₁₂		X						
hsCRP		X						
Ferritin and TSAT		X						
Iron status markers ¹²			X	X	X	X	X	
Indices of erythropoiesis ¹³			X	X	X	X	X	
Blood draw for PGx			X					
AE and SAE Assessment ¹⁴	X ¹⁵	X ¹⁵	X	X	X	X	X	X
Review Concomitant Medications	X	X	X	X	X	X	X	X

- ¹ Allowable time window \pm 3 days.
- ² Allowable time window \pm 2 days.
- ³ All assessments to be performed **PRIOR** to crossing over.
- ⁴ Criteria to be assessed can be found in Section 9.4.1.
- ⁵ Complete physical examination, medical history & demography to be performed at Week -4, while a brief physical examination to be performed at Week -2 and Day 1.
- ⁶ Local urine testing will be standard for the protocol unless serum testing is required by local regulation or IRB/IEC.
- ⁷ As detailed in Inclusion Criteria.
- ⁸ Participants that had been administered daprodustat during treatment Period 1 will be switched to rhEPO, while those on rhEPO will be switched to daprodustat. Examples on switching are provided in the Study Reference Manual (SRM).
- ⁹ Height is only collected at Week -4.
- ¹⁰ Clinical laboratory assessments guidance can be found in Section 9.4.5
- ¹¹ Liver chemistry monitoring guidance can be found in Section 9.4.6.
- ¹² Iron status markers include serum iron, ferritin, transferrin, transferrin saturation (TSAT), soluble transferrin receptor, hepcidin and erythroferrone and are described in Section 9.8.2. All samples for iron status markers to be taken pre dose.
- ¹³ Indices of erythropoiesis include Hgb, hematocrit, red blood cell number, mean corpuscular volume, reticulocyte Hgb and reticulocyte number and are described in Section 9.8.3.
- ¹⁴ Guidance on the timing and need for collection of AEs & SAEs are described in Section 9.2.
- ¹⁵ SAEs assessed as related to study participation or a GSK product are collected at this visit. See Section 9.2.1 for additional details.

- The timing and number of planned study assessments, including safety or biomarker assessments may be altered during the course of the study based on newly available data to ensure appropriate monitoring.
- Any changes in the timing or addition of time points for any planned study assessments must be documented and approved by the relevant study team member and then archived in the sponsor and site study files but will not constitute a protocol amendment. The IRB/IEC will be informed of any safety issues that require alteration of the safety monitoring scheme or amendment of the ICF.

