5.1. Overall Design

This study will be a randomized, repeat dose, open label, two period cross-over study in adult, male and female participants with anemia associated with chronic kidney disease who are not on dialysis currently treated with stable doses ($\leq 50\%$ change in 4-weekly dose) for at least 8 weeks prior to and including the screening period, of rhEPO (i.e., epoetin alfa or darbepoetin alfa).

Sufficient participants will be enrolled such that at least 12 participants comprise the Evaluable Population (See Section 10.3.1.3).

The study design is outlined in Figure 2.

Figure 2 Study Design

- There will be a 4-week screening period in order to confirm that participants have stable Hgb levels and to assess entry criteria
- A 28-day Treatment Period 1 for incorporation of iron into erythrocytes while on randomized study treatment
- A 28-day Treatment Period 2 for a second incorporation of iron into erythrocytes while on randomized study treatment
- A follow-up visit 14 ± 3 days after completing treatment.

Participants will be randomly assigned either to remain on their current therapy (either epoetin alfa or darbepoetin alfa) or be switched to daprodustat for Treatment Period 1. For assessment of incorporation of iron into erythrocytes, enrolled participants will be administered ferrous sulfate containing a stable isotope of iron (^{57}Fe or ^{58}Fe) orally in a randomized fashion following 2 weeks of administration of randomized study treatment. Thus, there are 4 possible treatment sequences as shown in Table 1. Two weeks following oral iron administration a blood sample will be taken in order to assess the incorporation of the iron isotope into red blood cells by thermal ionization mass

spectrometry (TIMS) using published methods (IAEA Human Health Series No. 21, 2012).

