5.4. Scientific Rationale for Study Design

This study will use a randomized, repeat dose, open label, two period cross over design in adult, ND, male and female participants with anemia associated with chronic kidney disease currently treated with stable rhEPO doses ($\leq 50\%$ change in 4-weekly dose) for at least 8 weeks prior to and including the screening period.

- This will be an open label study as oral iron absorption is an objective measure and unlikely to be influenced by the participant's knowledge of the treatment administered. Additionally, blinding of treatment would be difficult as rhEPO is

- administered by subcutaneous injection, while daprodustat is administered orally once daily as a tablet.
- Iron absorption will be assessed over a 2 week period commencing after 2 weeks of study treatment, a period of time when it is anticipated that any changes in oral absorption mediated by changes in expression of HIF-dependent DcytB and DMT1 will be apparent ([Shah, 2009](#)).
 - This study will use a cross over design, with oral iron absorption assessed in each participant following both rhEPO and daprodustat administration, in order for each participant to serve as their own control.
 - Participants will need to be currently treated with stable doses ($\leq 50\%$ change in 4-weekly dose) of rhEPO for at least 8 weeks prior to and including the screening period. Additionally, participants need to have stable Hgb levels for the 4 weeks of screening. Finally, participants will be switched from their current rhEPO to daprodustat using a switching algorithm that was designed to result in no change in Hgb levels. All of these aspects are intended to minimize any potential for a change in erythropoiesis during the course of the study in order to minimize any potential change in oral iron absorption due to a change in erythropoiesis ([Skikne, 2000](#)).
 - The planned population is participants currently on rhEPO for anemia associated with chronic kidney disease that are non-dialysis dependent. This population was chosen as those most likely to be administered oral iron therapy for the treatment of anemia. Additionally, as oral iron is inferior to IV iron likely due to elevated levels of hepcidin and pro-inflammatory cytokines that restrict intestinal iron absorption, this is the population most likely to benefit from an increase in oral iron absorption ([Macdougall, 2016](#)).

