 - This study uses iron incorporation into erythrocytes in order to assess oral iron absorption. While it is appreciated that changes in erythrocyte iron content can be due to many factors, erythrocyte iron content is a well-recognized surrogate for iron absorption ([IAEA Human Health Series No. 21, 2012](#)). Additionally, fractional iron absorption as an endpoint allows for comparison to studies in non-anemic participants.
 - At present, three methodologies are primarily recognized for assessing fractional iron absorption: fecal recovery of the ingested isotope, plasma appearance of the ingested isotope and iron incorporation into erythrocytes following oral ingestion. Of the three, the most frequently used approach is iron incorporation into erythrocytes using single or multiple oral labels as it is more sensitive than either the fecal recovery or plasma appearance methods ([IAEA Human Health Series No. 21, 2012](#)). The majority (80%) of the iron that is absorbed is incorporated into red blood cells in Hgb, a process which occurs over 10 to 12 days. Once incorporated, the iron is stable for the lifespan of the red blood cell, a period of up to 120 days in non-anemic participants and approximately 70 days in individuals with chronic kidney disease.
 - Iron absorbed from the diet is obtained from animal-based sources, and is known as heme iron, while plant-based iron is non-heme iron. This study will assess the

absorption of non-heme iron as most of the understanding of iron absorption is related to non-heme iron which typically comprises the majority of dietary and supplemental iron.

- ND-CKD patients which have elevated levels of C-reactive protein (CRP) and hepcidin typically experience poor intestinal iron absorption ([Macdougall, 2014](#)). Therefore, hsCRP will be assessed at screening for eligibility in order to minimize the recruitment of participants with poor intestinal iron absorption due to inflammation.
- Finally, stable isotopic iron will be administered in the fasted state as the fraction of iron absorbed in the fasted state is typically much higher than that which occurs when a component of a mixed meal. A recent publication using this methodology in 18 healthy, adult female participants reported an average absorption \pm SD of $14.71 \pm 10.7\%$ in the fasted state compared to $3.63 \pm 6.5\%$ in the fed state ([Young, 2009](#)). In this regard, it is considered that a 30% change in oral iron absorption is clinically relevant.

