7	Total incorporated iron isotope (mg)	$Total\ incorporated\ ^{58}Fe = Parameter5 * Parameter6 * 0.0214 * 0.50797$	$Total\ incorporated\ ^{57}Fe = Parameter5 * Parameter6 * 0.0214 * 0.49203$	S&P will derive this value. We assume

S. No.	Parameters	Period 1 - ⁵⁸ Fe Fractional Oral Iron Absorption	Period 2 - ⁵⁷ Fe Fractional Oral Iron Absorption	Details
				the fractional abundance of ⁵⁷ Fe in mg is (0.0214 g * 0.01), and the fractional abundance of ⁵⁸ Fe in mg is (0.00287 g * 0.01).
8	% iron isotope incorporated	$\% \text{ } ^{58}\text{Fe Incorporated} = \frac{\text{Parameter7}}{58\text{Fe Dose}}$	$\% \text{ } ^{57}\text{Fe Incorporated} = \frac{\text{Parameter7}}{57\text{Fe Dose}}$	S&P will derive percent of iron isotope incorporated. ⁵⁷ Fe and ⁵⁸ Fe doses (mg) will be determined using the

S. No.	Parameters	Period 1 - ⁵⁸ Fe Fractional Oral Iron Absorption	Period 2 - ⁵⁷ Fe Fractional Oral Iron Absorption	Details
				density of ferrous sulfate (FeSO ₄) oral solution (1g/mL), the dose of oral solution (in mL), and concentration of elemental iron (1mg/mL).
9	Assumed % iron isotope absorbed if 80%	$\% \text{ } ^{58}\text{Fe absorbed} = \text{Parameter8} * \frac{100}{80}$	$\% \text{ } ^{57}\text{Fe absorbed} = \text{Parameter8} * \frac{100}{80}$	S&P will derive this value, using the formula suggested by the IAEA for the assessment

S. N o.	Para meter s	Period 1 - ⁵⁸ Fe Fractional Oral Iron Absorption	Period 2 - ⁵⁷ Fe Fractional Oral Iron Absorption	Detail s
				of iron bioavailability (IAEA pg.38). Parameter 9 defines the fractional oral iron absorption endpoint, assuming 80% of the absorbed Fe is incorporated into RBCs.

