6.2.4. Assessment Window

For data summaries by visit, scheduled visits with nominal visit description will be displayed. Unscheduled visits will not be displayed or slotted into a visit window but will be included in the derivation of worst-case post baseline assessment. All un-scheduled visits will be displayed in listings, as appropriate.

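### The ±2-day visit windows allow a tracer-to-sample interval of 10 or 11 days, which can end before red-cell incorporation is complete, so absorption can be slightly under-read

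*Protocol*

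**What the plan says.** The Schedule of Activities (protocol section 2) places "Administration of isotopic iron" at Days 15 and 43 and "Blood sampling for isotopic iron" at Days 29, 43 and 57. Footnote 2 sits on the treatment-period header and covers all of these visits: "Allowable time window \pm 2 days".

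Protocol 5.1 describes the interval in words: "Two weeks following oral iron administration a blood sample will be taken in order to assess the incorporation of the iron isotope". It gives no tolerance or minimum. Protocol 5.4 repeats the plan ("Iron absorption will be assessed over a 2 week period commencing after 2 weeks of study treatment") and describes incorporation of absorbed iron into red cells as "a process which occurs over 10 to 12 days".

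SAP 4.2.1 converts incorporated iron to absorbed iron by a factor of 100/80, "assuming 80% of the absorbed Fe is incorporated into RBCs". The actual number of days between tracer and sample does not enter the derivation. The Evaluable Population (protocol 10.3.1.3, SAP section 3) requires a completed absorption assessment in both periods and says nothing about its timing. The only sensitivity analysis of the primary endpoint (SAP 4.2.3) changes the analysis population, not the timing of the values used.

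**The concern.** The nominal 14 days leaves a margin of 2 days over the longest incorporation time the protocol gives. Two separate ±2-day windows can together remove 4 days. A site can then comply with the schedule and still sample while label is entering the red cells. The resulting error can only go downward, and the fixed 100/80 factor does not correct it.

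The primary comparison is within participant, with 12 pairs planned. A short interval in one period and an adequate one in the other would put a false difference into that pair. No later measurement recovers the loss. The Day 43 sample could show late incorporation of the Period 1 label, but the SAP uses it only as the isotope baseline for Period 2. Period 2 has no isotope sample after Day 57.

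**Working it through.** **Inputs.** Tracer on Days 15 and 43, samples on Days 29 and 57, window ±2 days (protocol section 2). Incorporation takes 10 to 12 days, fasted absorption in the cited study of healthy women was 14.71%, and a 30% change is called clinically relevant (protocol 5.4). Sample size is 12, difference 11 points, SD 10.7 points (protocol 10.2).

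**1. The plan's own figures.** 29 − 15 = 14 and 57 − 43 = 14, which matches the stated two weeks. A paired t-test with n = 12, difference 11, SD 10.7 and two-sided 5% has power 89.9%, which matches the stated 90%. The 5% level is inferred from the 95% confidence interval.

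**2. Allowed interval if each visit moves separately.**
- Shortest: Day 17 to Day 27, or Day 45 to Day 55, is 10 days.
- Longest: Day 13 to Day 31, or Day 41 to Day 59, is 18 days.
- If the window were instead counted from the actual tracer date: 14 ± 2 = 12 to 16 days.

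**3. How often it is short.** Whole-day shifts from −2 to +2 at both visits give 25 combinations. One gives 10 days and two give 11 days. If all are equally likely (assumption), 3/25 = 12% fall below 12 days, or 24 × 0.12 = 2.9 of the 24 values from 12 participants.

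**4. Loss for a single value.** The documents give no incorporation curve. Assume label enters the red cells linearly from dosing and is complete at day T. The fraction read at day d is then min(1, d/T).

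| Interval d | T = 10 | T = 11 | T = 12 |
|---|---|---|---|
| 10 days | 0% | 9% (1.34 points) | 17% (2.45 points) |
| 11 days | 0% | 0% | 8% (1.23 points) |
| 12 days or more | 0% | 0% | 0% |

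Points are on 14.71%; for example, 14.71 × 10/12 = 12.26, a loss of 2.45. For scale, 30% of 14.71 is 4.41 points. That figure refers to a change in absorption, whereas the table gives the error in one value, so the two are not directly comparable.

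**5. Effect on the trial, with T = 12 and uniform shifts.**
- Mean loss: (1 × 1/6 + 2 × 1/12)/25 = 1.33% relative, or 14.71 × 0.0133 = 0.2 points.
- Attenuated difference: 11 × (1 − 0.0133) = 10.85 points.
- Variance of the loss fraction: (1/36 + 2/144)/25 − 0.0133² = 0.00149. With arm means of 14.71 and 25.71 (14.71 + 11), the added variance of a paired difference is 0.00149 × (14.71² + 25.71²) = 1.31. The SD becomes √(10.7² + 1.31) = 10.76. Allowing also for a between-participant SD of 10.7 in each arm gives 10.78.
- Power at a difference of 10.85 and an SD of 10.75 to 10.78: 88.7% to 88.9%, about one point below 89.9%.

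**The case against.** **The window may be meant to run from the tracer.** For the follow-up visit, protocol 5.1 counts the tolerance from the final blood sample. It also defines the isotope sample relative to oral iron administration. If footnote 2 is read in the same way, the interval is 12 to 16 days and the problem disappears. This reading is possible, but it is not written. The footnote covers all treatment-period visits, most of which have no such anchor. The Study Reference Manual may set an interval, but it is not among the documents and cannot be assumed to do so.

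**Ten days may be enough.** Ten days lies inside the protocol's range, so the loss can be zero. This stands: a short interval *can* under-read, and only in participants whose incorporation takes longer than that interval. Long intervals do no harm on the protocol's own account, because incorporated iron stays put for about 70 days in chronic kidney disease.

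**The effect is small.** This also stands. Under the assumptions above, 22 of 25 combinations lose nothing.

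**SAP 6.2.4 does not govern the primary model.** Its rule opens "For data summaries by visit, scheduled visits with nominal visit description will be displayed" and concerns visit summaries. It should not be read as barring the use of actual dates. In-clinic dosing dates and times are recorded (protocol 7.6), so actual intervals can be derived. What is missing is any planned use of them.

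**Conclusion.** The point holds as a cheap improvement. On the ordinary reading of footnote 2, a compliant interval can be 10 to 18 days. Intervals of 10 or 11 days can end before incorporation is complete by the protocol's own figure, and nothing in the derivation or the analysis sets picks this up. The trial-level figures rest on uniform visit shifts and on linear incorporation complete at day 12. Neither assumption comes from the documents, and with completion by day 10 there is no loss at all.

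A reader might go further in two ways that the documents do not support:
- **Bias towards one treatment.** The windows are identical for both treatments and both periods, and no reason is given for short intervals to cluster in one arm. The expected result is noise and slight attenuation.
- **Carryover from a short lead-in.** In Period 2 the crossover and the tracer visit can both move, so the days on the new treatment before the tracer can also fall to 10 (Day 31 to Day 41). Protocol 5.4 anticipates that changes will be apparent after two weeks, but nothing shows that 10 days is inadequate, and no size can be put on it. At most, the actual days on treatment before each tracer should be reported.

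**What to change.** **Protocol, Schedule of Activities, footnote 2.** Add that the Day 29 and Day 57 isotope samples are drawn within the existing ±2-day window and no earlier than 12 days after the recorded tracer date. This fits the present schedule. A tracer on Day 17 leaves Days 29 to 31 for the sample, and a tracer on Day 45 leaves Days 57 to 59. A tracer on or before the nominal day is unaffected, since Day 15 to Day 27 is already 12 days. The rule removes only the 3 short combinations out of 25. A 14-day minimum or a chain of one-sided windows is not needed: it would exceed the protocol's 12-day figure and could lengthen Period 1.

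**SAP 4.2.1 and 4.2.3.** Derive the actual tracer-to-sample interval for each value. Pre-specify a sensitivity analysis of the primary endpoint that leaves out values with an interval under 12 days. This can still be added before analysis if visits can no longer be changed.

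**Cost.** One footnote clause and one or two SAP sentences, using dates already collected. Scheduling is slightly less flexible when the tracer is given late, and the sensitivity analysis may have fewer complete pairs.
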